8.3.1 Allowed Interventions

The interventions in this study are a patient-facing “Healing after Surgery Guide” and a clinical team-facing clinical decision support augmented by existing, vetted patient education materials already consistent with the scope of work for perioperative care. These interventions could prompt utilization of NPPC modalities prior to, during, and after the hospital stay.

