9.2.2 Inpatient Stay Touchpoints

Touchpoint 3 – Acute Hospital Care

Nursing and physical/occupational therapy staff will offer patients the opportunity to receive preference-concordant NPPC modalities during their

hospital stay. For self-administered practices, staff will validate patients' preferences and ensure the availability of needed supplies, instruction and ambient conditions (e.g. privacy).

If patients are not experiencing adequate pain relief, they will be prompted by nurses to try alternative NPPC modalities in order to raise awareness of opioid harms, and enhance clinician support for patients' NPPC use. Additionally, NPPC nurse and physician specialists will be "on call" to assist unit nurses, therapists, and members of the surgical care team in how to optimize the safety and effectiveness of NPPC modalities for specific patients.

Touchpoint 4 – Hospital Discharge

During the discharge process, patients will be asked to revise their NPPC plan, as needed based on their preferences and responses to specific NPPC modalities, and provided with support and resources. Discharge planning will include facilitation of continuation of patients' NPPC use in their post-acute care settings (e.g. home, rehabilitation facility, etc.). Patients will be given prescriptions to receive local NPPC, if available and/or appropriate.

Patients' discharge summaries will be auto-populated with selection-concordant NPPC instructions and resources to find local NPPC providers.

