10.1 Specification of Safety Parameters

There are no pre-specified safety parameters, as they are not-applicable to the intervention being studied. This study engages patients in strategies for post-surgery pain management that conform to guideline-based care, all of which have far lower risk profiles (almost zero risk) and greater benefit-to-risk ratio compared to usual post-surgical pain management that involves opioid medications. Patients whose pain cannot be sufficiently managed with non-pharmacological pain management strategies will be supported by their surgical team (with assistance from pain management clinicians, as needed) using conventional pain management strategies.

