10.2 Methods and Timing for Assessing, Recording, and Analyzing Safety Parameters

Our interventions are informational and logistical and designed to enhance safe, patient-centered approaches to patient care. If they were to prompt, for instance, less opioid use, in theory, that could lead to worse function or increase pain. That is why we chose the composite outcome measure of pain and physical function. Whether it is accurate to associate that “risk” to our intervention itself, versus the treatments prompted by our intervention is a topic of debate. Nevertheless, this is a minimal risk study. If we conservatively assume that downstream prescribing practices are attributable to our interventions, usual care (using opioid medications as a first line approach to pain management in the acute and post-acute recovery periods following a surgical procedures) introduces greater risk of dependency, addiction, and overdose, than those posed by the intervention we are providing in the NOHARM trial which is guideline concordant.

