10.3 Adverse Events and Serious Adverse Events

Adverse Event (AE): Any untoward or unfavorable medical occurrence resulting unambiguously from the misuse or overuse of non-pharmacological pain management strategies facilitated by the intervention. All untoward or unfavorable medical occurrences will be first assumed to be associated with the patient’s surgery. Untoward or unfavorable medical occurrences will be deemed an adverse event only if they can be clearly associated with use of non-pharmacological pain management strategies recommended and/or facilitated by the intervention and could not, under any circumstances, have otherwise happened.

Serious Adverse Event (SAE): Any adverse event unambiguously associated with the intervention that:

- Results in death

- Is life threatening, or places the participant at immediate risk of death from the event as it occurred
- Requires or prolongs hospitalization
- Causes persistent or significant disability or incapacity
- Results in congenital anomalies or birth defects
- Is another condition which investigators judge to represent significant hazards

There are no laboratory or other clinical values which may be used to assess safety concerns related to the intervention. Patient reported pain, requests for assistance with pain management, and other health outcomes, while measurable, are associated with the patient's surgical procedure and will be gathered as part of the ultimate outcome data. If patients were to experience a paradoxical response to a modality –massage, for example – those effects would likely be transient and they would have access to all the usual care resources of Mayo Clinic as any other patient should those symptoms persist.

Adverse events that may be anticipated in the study involve any patient misuse or overuse of non-pharmacological pain management strategies. Patients who elect to incorporate non-pharmacological pain management strategies in their recovery from surgery will be instructed in the use of those strategies, including whether (and when) the use of those strategies is appropriate in their situation.

Because non-pharmacological pain management modalities recommended by the intervention are guideline concordant approaches to pain management under normal circumstances, they will be monitored by the patient's surgical team as a part of usual post-acute care. Therefore, we will not actively review for potential events with scheduled promptings.

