Appendix B: Resource List

Patient Support

- Zoom group support calls will help patients by answering questions about the patients' selected modalities. Answers will be provided by NOHARM trial staff. Resources include:
 - [Zoom Group Call Instructions](#)
 - [Welcome Instructions](#)
 - Zoom Group Call Talking Points
- Toll-free number ([name]) will help support patients by answering questions about the patients' selected modalities and the NOHARM trial staff will provide answers
- Healing After Surgery Website (www.healingaftersurgery.mayoclinic.org was developed to support patients who are portal users)
- [Healing After Surgery Workbook was developed to support patients, who may not be portal users, may not have access to a computer or to the internet or may not be comfortable with technology](#)
 - [Workbook Cover Letter](#)
- [Transcutaneous Electrical Nerve Stimulation \(TENS\) Patient Education Video](#) is a 5-minute patient education instructional video
- 13 Modality videos. Each video provides a brief modality overview
- [Modality Flyers](#) Each flyer [provides a brief overview of each modality and resource list](#)
- [Rack Card - Healing After Surgery Managing Pain is a quick reference guide \(rack card\) about NOHARM and the NOHARM resources](#)
- [Healing after Surgery DVD](#) includes all patient education video content used in the NOHARM intervention. The DVD mirrors what is on MCTV.
- [Mayo TV NOHARM Resource List provides the NOHARM patient education resources available on Mayo Clinic Television \(MCTV\)](#)
- [NOHARM TENS units: the NOHARM trial will purchase TENS units for the surgical clusters](#)
- [Portal messages](#)
 - Pre-op sending/assignment of Healing after surgery guide: message sent when the patient is assigned the Healing after surgery guide
 - Pre-op Healing after surgery guide non-response reminder message: if the patient hasn't completed the Healing after surgery guide, this reminder is sent.
 - Pre-op post-Healing After Surgery Guide follow-up message/Thank you (4 confidence): 4 messages based on the patient's response to the confidence questions.
 - Post-Op Discharge ("Welcome Home") Message: reminds patients of NOHARM resources after they are discharged from the hospital.
 - 1, 2 and 3 month post-op questionnaire reminder (send 4 days after initial questionnaire was sent): Standard Epic reminder message

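### Section 10 does not account for the TENS units the trial buys, and its adverse event scope contradicts itself on whether harm from a modality used as instructed is reportable

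*Combined protocol and SAP*

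**What the plan says.** Under Patient Support, Appendix B lists: "NOHARM TENS units: the NOHARM trial will purchase TENS units for the surgical clusters". The same list has a TENS video, which "is a 5-minute patient education instructional video". TENS is mentioned nowhere else in the text supplied. Section 8.3.1 describes the intervention as the Guide plus "clinical team-facing clinical decision support augmented by existing, vetted patient education materials already consistent with the scope of work for perioperative care". Section 9.2.2 has inpatient staff "ensure the availability of needed supplies, instruction and ambient conditions", without naming a device.

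On safety, section 10.2 says: "Our interventions are informational and logistical and designed to enhance safe, patient-centered approaches to patient care". Section 10.1 says: "There are no pre-specified safety parameters, as they are not-applicable to the intervention being studied". Section 10.3 opens its definition of an adverse event with "Any untoward or unfavorable medical occurrence resulting unambiguously from the misuse or overuse of non-pharmacological pain management strategies facilitated by the intervention". Later in the same paragraph, an occurrence is deemed an adverse event "only if they can be clearly associated with use of non-pharmacological pain management strategies recommended and/or facilitated by the intervention" and if it could not have arisen in any other way. Section 10.3 also says that there will be no scheduled active review for events.

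**The concern.** The safety section reads as though the trial supplied only information, prompts and support, while the resource list shows that it also buys a device. A person can come to harm from a device, or from a hands-on modality, while following the instructions. That is neither misuse nor overuse, so three of the sentences that set the scope of reporting would leave it out.

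The trial has no patient exclusions (section 7.2), seeks a waiver of consent on minimal-risk grounds (section 14.2), and describes the modalities as carrying almost no risk (section 10.1). Section 13.3.4 treats failure to monitor patient safety as a protocol deviation. If the counting rule can leave out harm during instructed use, a low or zero count says little about whether the risk statement is true.

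**Working it through.** There is no figure to reproduce. The check is a comparison of the passages.

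**Is TENS part of what the trial delivers?** Appendix B says that the trial buys the units. Section 8.1.1 points to Appendix B for the resource list, so the intervention section reaches the units by reference. Section 10 does not reach them at all. The documents do not say who receives a unit, or whether units stay on the ward or go home.

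**Statements limited to misuse or overuse (all in section 10.3):**
1. The first sentence of the adverse event definition.
2. The sentence on which adverse events may be anticipated.
3. The sentence telling surgical teams what to report to the study team.

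**Statements without that limit:**
1. The later sentence of the definition, which refers to use of modalities recommended or facilitated by the intervention.
2. The trigger in section 10.3.1, under which a surgical or study team member may suspect an event when a medical issue is unambiguously related to the patient's interaction with the intervention.

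**Can the two sets be read together?** The later sentence of the definition is worded as a condition that must be met (only if), so it does not clearly widen the first sentence. A strict reader requires both and excludes instructed use. A generous reader takes the later sentence as the operative rule and includes it. The text supports either reading.

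**Does the wider route in 10.3.1 and 10.3.2 settle it?** Section 10.3.2 documents every suspected event. Under 10.3.1, however, reporting follows only once the event is found to be an adverse event by the protocol definition. The coordinator's recording duty in 10.3.2 likewise refers back to the definitions above it. Both steps return to section 10.3, where the contradiction lies. A suspected event could be noted and then adjudicated out.

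**Would another source pick it up?** Active review is ruled out, so unprompted reports matter most, and the surgical teams' stated duty is one of the limited sentences. Section 10.3 also discusses a paradoxical response to a modality, with massage as the example. It leaves this to usual care and gives no recording rule.

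**Is there a denominator?** Section 12.4.2 takes inpatient use of specific modalities from flowsheets, and asks patients at 1, 2 and 3 months which modalities they have used. Section 12.5 counts 14 modalities. Appendix B lists 13 modality videos and one TENS video, and 13 + 1 = 14. That suggests TENS is the fourteenth, but it is an inference. If it is right, TENS users are captured, apart from patients who do not respond and have no flowsheet entry. Issue of a trial-purchased unit is not a listed variable.

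**The case against.** The strongest reply is that the protocol is wider than its first sentence suggests, and much of that reply stands. Four stronger readings are tempting, and the documents do not support them.

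- *Harm from instructed use would never be recorded, or device events would be zero by definition.* The definition also says use, the trigger in 10.3.1 is not limited to misuse, and 10.3.2 documents suspected events. What remains is that such an event may go unreported as an adverse event.
- *The protocol claims a purely informational intervention.* Section 10.2 says informational and logistical, and goes on to ask whether risk from treatments prompted by the intervention should be attributed to it. Its example there is worse pain or function after less opioid use, so a supplied device is still not considered. Nor does the absence of safety parameters rest on that description. Section 10.1 argues from guideline concordance and the low risk of the modalities.
- *There is no denominator.* Modality use is collected by flowsheet and self-report. Only issue of a unit is missing.
- *Cardiac or obstetric patients face a particular TENS hazard.* The documents give no such hazard. Section 10.3 says that patients will be instructed whether and when a strategy suits them, and section 9.2.2 provides on-call specialists.

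It can also be said that the Data and Safety Monitoring Plan and the safety board charter, both listed in Appendix B, may deal with devices. They were not supplied, so this cannot be excluded. Even if they do, the definition in section 10.3 would still contradict itself.

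**Conclusion.** The point holds in a limited form. Section 10 takes no account of the TENS units the trial buys, and three sentences of section 10.3 conflict with a fourth and with section 10.3.1 on whether harm during instructed use is an adverse event. Because reporting runs through the protocol definition and there is no active review, the conflict could lead to under-counting, and a low count could not support the near-zero risk statement.

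No number of missed events can be given. The documents state no number of units, no TENS uptake and no harm rate, and any figure would rest wholly on assumed rates. The conclusion rests on the text alone and assumes that the monitoring plan does not override section 10.3. It calls for a correction of wording and does not show that patients are being harmed.

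**What to change.** 1. In section 10.3, replace *misuse or overuse* with *use, including use as instructed, misuse or overuse* in the lead definition, the anticipated-event sentence and the surgical-team reporting sentence. All three then agree with the later sentence of the definition and with the trigger in 10.3.1.
2. In section 10.2, acknowledge that the trial supplies TENS units.
3. State whether TENS is one of the 14 modalities. If it is, report TENS-related events to the safety board against TENS users from the flowsheet and self-report data already collected.
4. Check the Data and Safety Monitoring Plan for consistency with the revised scope.

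The cost is a protocol wording change and a few more events to adjudicate, with no change to patient care. No separate TENS safety parameter is needed for this. The change removes the contradiction in scope, but it leaves the near-absolute causality test and the lack of active review in place. A low count should still be reported with those limits stated.
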